### 6.1 STUDY INTERVENTION(S) ADMINISTERED

**Table 2 - Overview of study interventions administered**

ARM name	Dupilumab 200 mg	Placebo
Intervention name	Dupilumab 200 mg	Placebo matching dupilumab 200 mg
Type	Biological	Other
Dose formulation	Dupilumab 200 mg: a 175 mg/mL dupilumab solution in a prefilled syringe to deliver 200 mg in 1.14 mL	Placebo matching dupilumab 200 mg will be supplied as an identical formulation to the active 200 mg formulation without dupilumab, in a prefilled syringe to deliver placebo in 1.14 mL
Unit dose strength(s)	200 mg	0 mg
Dosage level(s)	200 mg every 14 ±3 days after an initial loading dose of 400 mg	0 mg every 14 ±3 days after an initial loading dose of 0 mg
Route of administration	SC injection a	SC injection a
Use	experimental	placebo- comparator
IMP and NIMP	IMP	IMP
Packaging and labeling	One glass prefilled syringe packed in a participant kit box. Both glass prefilled syringe and box will be labeled as required per country requirement.	One glass prefilled syringe packed in a participant kit box. Both glass prefilled syringe and box will be labeled as required per country requirement.
Current/Former name(s) or alias(es)	Dupixent	

a SC injection sites should alternate between the upper thighs, 4 quadrants of the abdomen or the upper arms, so that the same site is not injected twice during consecutive administrations. Injection in the upper arms can only be done by a trained person (caregiver) trained by Investigator or Delegate) or health care professional but not the participants themselves.

IMP: investigational medicinal product; SC: subcutaneous.

In specific situations, between the protocol-scheduled on-site visits, interim visits may be required for IMP dispensing. As an alternative to the on-site IMP dispensing, IMP may be supplied from the site to the participant via a Sponsor-approved courier company where allowed by local regulations and approved by the participant.

For participants enrolled through virtual site (Metasite), IMP will be supplied from the virtual site to the participant via DTP service which will be handled and under the responsibility of Science37. For a regional or national emergency declared by a governmental agency that results in travel restrictions, confinement, or restricted site access, contingency measures are included in Appendix 8 ([Section 10.8](#)).

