## **6.3 MEASURES TO MINIMIZE BIAS: RANDOMIZATION AND BLINDING**

### **Randomization**

A randomized intervention kit number list will be generated centrally by Sanofi. The IMP (dupilumab or placebo) will be packaged in accordance with this list.

The Sanofi Clinical Supplies team will provide the randomized intervention kit number list and the Study Biostatistician will provide the randomization scheme to the centralized intervention allocation system. This centralized intervention allocation system will generate the participant randomization list according to which it will allocate the intervention to the participants.

The Investigator obtains intervention kit numbers at randomization (Visit 2) and subsequent scheduled visits via an IVRS/IWRS that will be available 24 hours a day.

Science37 Metasite: The investigator of Metasite obtains intervention kit numbers at randomization (Visit 2) and subsequent scheduled visits via IVRS/IWRS. Science37 participant randomization in IVRS/IWRS will occur on Day 1, with first loading dose occurring up to 5 days post randomization to account for the lag between IVRS/IWRS randomization trigger for IMP DTP shipment and IMP availability to participant/mobile study nurse.

Science37 participant windows increased up to 3 days (the maximum visit window) for the subsequent at home dosing visits (week 4, week 8, week 12), to account for the lag between IVRS/IWRS trigger for IMP DTP shipment and IMP availability to participant/mobile study nurse.

Participants who meet the entry criteria will be randomized to receive either dupilumab or placebo. Participants will be randomized centrally using a 1:1 randomization ratio for dupilumab 200 mg Q2W and placebo Q2W. Randomization will be stratified according to 5 strata: one stratum for all participants included in the [REDACTED] (regardless of dose level of ICS, regardless of region) and 4 strata for participants not included in [REDACTED], according to region and ICS dose (Eastern Europe with high ICS dose, Eastern Europe with medium ICS dose, ROW with high ICS dose, and ROW with medium ICS dose). In total, no less than 40% participants need to be in “high ICS” strata, and no more than 25% participants need to be in “Eastern Europe” strata.

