Note: For participants randomized but not treated, the reference day will be the randomization date.

Intervals that are listed and/or tabulated in weeks will be transformed from days to weeks by using (without rounding) the following conversion formula:

$$\text{WEEKS} = \text{DAYS} / 7$$

Intervals that are listed and/or tabulated in months will be transformed from days to months by using (without rounding) the following conversion formula:

$$\text{MONTHS} = \text{DAYS} / 30.4375$$

The last on-treatment value of safety parameters is the final measurement assessed during the treatment-emergent adverse event period regardless of the introduction of rescue therapy and including measurements at unscheduled visits.

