7.2.1. Extent of Exposure

The extent of IMP exposure will be assessed by the duration of IMP exposure.

Duration of IMP exposure is defined as last IMP dose administration date – first IMP dose administration date + 14 days, regardless of unplanned intermittent discontinuations.

Duration of IMP exposure will be summarized descriptively as a quantitative variable (number, mean, SD, median, Q1, Q3, minimum and maximum). In addition, duration of IMP exposure will also be summarized categorically by numbers and percentages for each of the following categories:

- >0 and ≤ 2 weeks
- >2 and ≤ 4 weeks
- >4 and ≤ 8 weeks
- >8 and ≤ 12 weeks
- >12 weeks

and cumulatively according to the following categories:

- ≥ 1 day
- >2 weeks
- >4 weeks
- >8 weeks
- >12 weeks

Additionally, the sum of the duration of IMP (total) exposure for all participants will be summarized by study intervention group and will be expressed in participant years.

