#20 Section 7.2.1 Extent of exposure. As definition for duration of exposure is taking into account last IMP + 14 days, the analysis by categories will be modified to capture appropriately the participants that took their treatment up to the end. The category “> 12 weeks” will be replaced by “>12 and <=14 weeks” and “>14 weeks” (and in cumulative analysis, category “>14 weeks” will be added)

#21 Section 5.1 Disposition. In the approved SAP, it is written: “A summary table to show participant disposition by visit according to trial impact (disruption) due to COVID-19 (visit not done, visit partially done on site, visit partially done by phone and visit done but delayed) will be provided overall and by country for the ITT analysis set”.

To avoid confusion with participants included in the subgroup [trial impact (disruption) due to COVID-19], it should be replaced as follows: “A summary table to reflect COVID-19 impact at each visit (visit not done, visit partially done on site, visit partially done by phone and visit done but delayed) will be provided overall and by country for the ITT analysis set”. And title of the corresponding table updated accordingly.

Signature Page for VV-CLIN-0655407 v1.0

lps16677-16-1-9-sap-addendum

Approve & eSign

Approve & eSign

Approve & eSign

Sanofi
Protocol: LPS16677

Dupilumab
Clinical study report

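### SAP Addendum #20 cuts exposure at exactly 14 weeks, the nominal duration of an on-time full course, so no category isolates participants treated to the end

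*SAP*

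**What the plan says.** SAP Section 7.2.1 defines exposure as "last IMP dose administration date – first IMP dose administration date + 14 days", and adds that this applies "regardless of unplanned intermittent discontinuations". It tabulates duration in bands with upper limits of 2, 4, 8 and 12 weeks and an open band above 12 weeks, plus cumulative rows from at least 1 day up to >12 weeks.

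SAP Section 4.4.6 sets the unit conversion: "Intervals that are listed and/or tabulated in weeks will be transformed from days to weeks by using (without rounding) the following conversion formula", namely days divided by 7.

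Addendum #20 notes that the definition adds 14 days to the last dose. It replaces the open band with two, >12 to ≤14 weeks and >14 weeks, and adds a cumulative >14 weeks row. The reason given is that "the analysis by categories will be modified to capture appropriately the participants that took their treatment up to the end".

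The dosing schedule comes from elsewhere. SAP Section 3.3 has one injection every two weeks until Week 12. Protocol Table 2 gives the regimen as "200 mg every 14 ±3 days after an initial loading dose of 400 mg". The protocol's Schedule of Activities puts ±3 days on the Week 4, 8 and 12 visits and shows dispensing at Week 12. Section 6.3 also treats Week 12 as a dosing visit for the virtual site.

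**The concern.** The addendum changes this table for one purpose, to show who was treated to the end. The new cut falls on the value that an exactly on-time full course produces. The existing 12-week cut falls on the value produced by stopping after an on-time Week 10 dose. With unrounded weeks and inclusive upper limits, one day either way moves a participant across a row.

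A reader of the clinical study report would probably take the top row as the completers. Many fully treated participants could be missing from it. The row below would mix completers with some participants who never had the Week 12 dose. The exposure table could then seem to disagree with the disposition and compliance tables.

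**Working it through.** **Inputs**
- Duration in days = (last dose date − first dose date) + 14: SAP 7.2.1.
- Weeks = days / 7, unrounded: SAP 4.4.6.
- Nominal dosing offsets from first dose of 0, 14, 28, 42, 56, 70 and 84 days: SAP 3.3.
- Window of ±3 days: Schedule of Activities for Weeks 4, 8 and 12; Protocol Table 2 for the interval.
- Category limits of 2, 4, 8, 12 and 14 weeks (14, 28, 56, 84 and 98 days), upper limits inclusive: SAP 7.2.1 and Addendum #20.

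**Duration by last dose taken**, applying ±3 days around each nominal day:

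| Last dose | Nominal days (weeks) | Range, days | Early or on time | 1 to 3 days late |
|---|---|---|---|---|
| Day 1 | 14 (2.00) | 14 | ≤2 | not applicable |
| Week 2 | 28 (4.00) | 25–31 | >2 to ≤4 | >4 to ≤8 |
| Week 4 | 42 (6.00) | 39–45 | >4 to ≤8 | >4 to ≤8 |
| Week 6 | 56 (8.00) | 53–59 | >4 to ≤8 | >8 to ≤12 |
| Week 8 | 70 (10.00) | 67–73 | >8 to ≤12 | >8 to ≤12 |
| Week 10 | 84 (12.00) | 81–87 | >8 to ≤12 | >12 to ≤14 |
| Week 12 | 98 (14.00) | 95–101 | >12 to ≤14 | >14 |

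The 4-, 8-, 12- and 14-week cuts each coincide with a nominal duration and split the participants who share that last dose. The 2-week cut does not: a single Day 1 dosing gives exactly 14 days, and the next possible duration is 25 days.

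**Cumulative rows.** The >12 weeks row contains every in-window Week 12 last dose (at least 95 days, above 84) but also late Week 10 last doses (85–87 days). The >14 weeks row contains only late Week 12 last doses. Neither equals the group treated to the end.

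**Size.** The documents give no distribution of dosing days. If all seven days from −3 to +3 are equally likely (an assumption), 4/7 = 57% of full-course participants fall in >12 to ≤14 weeks and 3/7 = 43% in >14 weeks. If all dose early or on time, 0% reach >14 weeks; if all dose late, 100% do. Under the same assumption 3/7 = 43% of those stopping after Week 10 fall in >12 to ≤14 weeks. That group is probably small. The plan expects 260 − 234 = 26 dropouts. If these spread evenly over the six possible earlier last doses (also an assumption), about 26/6 ≈ 4 stop after Week 10 and about 4 × 3/7 ≈ 2 share a row with completers.

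**A 13-week cut (91 days).**
- Longest duration for a Week 10 last dose: 70 + 3 + 14 = 87 days. Week 10 has no visit window of its own, so the interval can be compounded from a late Week 8 dose: 56 + 3 + 17 + 14 = 90 days. Both are below 91.
- Shortest duration for an in-window on-site Week 12 last dose: 84 − 3 + 14 = 95 days, above 91.
- Virtual site: the first dose may come up to 5 days after randomization. If Week 12 is counted from randomization, the shortest duration is 84 − 3 − 5 + 14 = 90 days, below 91.

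**The case against.** The strongest defence is that the inclusive upper limits work for exact dosing. An on-time Week 12 last dose (98 days) falls in >12 to ≤14 weeks, and an on-time Week 10 last dose (84 days) falls one row lower. On that reading >12 to ≤14 weeks is the planned-exposure row and >14 weeks is overrun. The addendum never says that completers belong in >14 weeks. This stands as a possible intention, but the permitted ±3 days break it at both ends: late completers leave the row and late Week 10 stoppers enter it.

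The information is also available elsewhere. Disposition (SAP 5.1) reports completion of treatment, and compliance (SAP 7.2.2) counts administrations and injections against plan. Exposure is also summarized as a continuous variable and in participant-years. All of this stands and limits the harm.

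Two stronger readings are tempting and should not be drawn. One is that timing rather than doses taken decides the category. It does not: within the ±3-day window the last dose confines a participant to at most two adjacent categories, so a Week 10 last dose cannot reach >14 weeks and an on-site Week 12 last dose cannot drop to ≤12 weeks. Timing only chooses between the two. The other is that the safety results rest on this table. They do not: adverse event percentages use the safety analysis set as denominator (SAP 9.1), and no safety summary uses the exposure categories.

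The 12-week cut also predates Addendum #20, which adds only the 14-week one.

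**Conclusion.** The point holds as a limited one. Addendum #20 does not meet its own stated purpose under either reading of the new rows, because the 12- and 14-week cuts are the nominal durations for last doses at Week 10 and Week 12. This follows from the SAP's definition, its unrounded conversion and the ±3-day window, and needs no distributional assumption. Only the 43%/57% split and the estimate of about 2 misplaced Week 10 stoppers rest on assumptions; the share of full-course participants in >14 weeks is otherwise bounded only by 0% and 100%. The 4- and 8-week cuts have the same property and the 2-week cut does not. The consequence is a blurred descriptive table, with nothing lost from the inferential or adverse event analyses.

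**What to change.** Replace the 12- and 14-week limits with one at 13 weeks, so that the last two rows are >8 to ≤13 weeks and >13 weeks, and add a cumulative >13 weeks row. Optionally move the 4- and 8-week cuts to 5 and 9 weeks (35 and 63 days), which lie in the gaps 31–39 and 59–67 days. Leave the 2-week cut.

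Add a footnote saying that >13 weeks identifies a last dose at Week 12, not that every dose was taken, since the duration ignores intermittent gaps. The footnote should also state from which date Week 12 is counted for the virtual site. About 10 participants were planned there, and one could fall at 90 days.

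The cost is SAP wording and row labels, with no new data or programming of substance. The one drawback is less alignment with any standard exposure categories the sponsor uses across studies; if that matters, keep the present rows and simply add the cumulative >13 weeks row.

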16.1.9.2 Other supporting statistical documentation

Not applicable since LPS16677 statistical documentation consists of SAP only.
